3.4.7 Correlative studies and pharmacodynamic assessments

Biopsies of palpable melanoma lesions and nodal metastases will be taken at baseline, on Cycle 1 Day 15 (\pm 3 days), and within 14 days of radiographic progression of disease. In addition, existing paraffin-embedded biopsy specimens will also be obtained for analysis and archival. Biopsies for patients with cutaneous, subcutaneous, and palpable nodal metastatic disease may be waived if the PI believes that such biopsies would pose an excessive risk to the patient. Imaging guided biopsies of other metastatic sites are optional and permitted in patients without visible or palpable disease unless the PI believes that such a biopsy would pose an excessive risk to the patient. For skin lesions, punch or core biopsies are preferred. For other lesions, core biopsies are preferred and an attempt should be made to obtain 3 cores if core biopsies are selected. Fine needle aspiration is permitted with punch or core biopsies if core biopsies are not feasible. At the time of tumor progression, biopsies should be taken from both progressing and non-progressing lesions if feasible.

Portions of all new tumor biopsy specimens will be immediately immersed in formalin and subsequently embedded in paraffin and additional tissue will be flash-frozen and stored at -70°C until the time of analysis. Paraffin embedded biopsies will be stored at room temperature. Pre-treatment melanoma tumor specimens will be analyzed by PCR to confirm the presence of a $\text{BRAF}^{\text{V600E}}$ or $\text{BRAF}^{\text{V600K}}$ mutation and to assess for concurrent mutations of NRAS. Specific correlative analyses are outlined below. Any remaining tissue specimens may be archived for future studies that may include but are not limited to nucleic acid sequencing, microarray analysis, and immunohistochemistry.

6-month PFS as a function of PTEN expression

Our hypothesis is that patients with PTEN loss at baseline will be more likely to survive for 6 months without disease progression. PTEN expression will be assessed as present or absent using immunohistochemical staining for PTEN. Pre-treatment tissue for PTEN IHC will be available for all patients (estimate N = 46) since the availability of pre-treatment tissue for BRAF

genotyping is required. PTEN staining in tumor specimens will be graded as “present” or “absent” for each patient by a collaborating pathologist. Attainment of 6 month PFS as a function of PTEN status will be assessed using Fisher’s exact test.

For PTEN and pS6 IHC, paraffin-embedded sections will be deparaffinized, rehydrated, and subjected to heat-induced antigen retrieval. Sections will be incubated with appropriate primary antibody (PTEN: Cell Signaling D4.3, 1:50 dilution; phospho-S6 Cell Signaling Polyclonal, 1:200 dilution) and incubated for 45 minutes. After overnight incubation with a secondary polyclonal rabbit antibody, slides will be developed using 3,3'-diaminobenzidine chromogen and counterstained with hematoxylin³⁹.

Change in phospho-S6 as a function of 6-month PFS

Our hypothesis is that patients surviving for 6 months without disease progression will demonstrate a larger decrease in PI3K pathway activity as assessed by IHC for phospho-S6 than those patients with disease progression or death prior to 6 months. The change in pS6 will be determined by comparing H-scores to quantify pS6 protein levels by IHC prior to treatment at after 8 weeks of treatment^{40,39}. The H-Score will be calculated for staining of tumor cells using the following formula; H-Score = (% at 0) * 0 + (% at 1+) * 1 + (% at 2+) * 2 + (% at 3+) * 3. Thus, this score produces a continuous variable that ranges from 0 to 300. The change in phospho-S6 staining will be determined as follows: $\Delta pS6 = (H_{4w} - H_0) / H_0$. Patients will be categorized based on whether or not they survived for 6 months without disease progression. $\Delta pS6$ over the first 8 weeks of treatment will be compared between the two groups using the Wilcoxon rank-sum test.

Gene expression profiles of PI3K and MAPK signaling in response and progression

Our hypotheses are: 1. Treatment response by RECIST v1.1 criteria after 8 weeks of treatment will be associated with an absence of PI3K and MAPK signaling as assessed by gene expression profiling and 2. Disease progression is associated with activation of either pathway. Gene expression profiling has emerged as an important tool for elucidating mechanisms of resistance to BRAF inhibitors in melanoma by identifying gene signatures of oncogenic pathway activation in an unbiased manner⁴¹. cDNA will be derived from RNA extracted from flash-frozen tissue specimens. Gene expression will be determined using GeneChip Human Gene 1.0 ST Arrays (Affymetrix) on cycle 3 day 1 (+/- 3 days) and within 7 days of determination of tumor progression. These profiles will be referenced to the profile of tumor tissue obtained prior to the initiation of treatment. Expression data will be normalized and background-corrected. Clustering will be performed with MeV 4.4. Differentially expressed genes will be identified using significance analysis of microarrays (SAM) with the R package. To identify and rank pathways enriched among differentially expressed genes, P-values (Fisher’s exact test) will be calculated for gene sets with at least 20% differentially expressed genes. Curated gene sets of canonical pathways including PI3K and MAPK in the Molecular Signatures Database (MSigDB) will be used as the comparator. Gene expression signatures consistent with MAPK, PI3K, or alternate pathways activation will be confirmed by RT-PCR and immunohistochemistry for phospho-protein levels such as pS6 and pERK. Our initial goal is to perform microarray analysis on matched biopsy specimens from a total of 10 patients: 5 who meet the 6 month PFS endpoint, and 5 with early disease progression within 4 months of the initiation of treatment. Until these patients have been identified, all patients with visible or palpable disease will undergo pre-

treatment biopsies. Additional biopsies and additional analyses may be performed at the discretion of the PI.

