
Note: A Brain MRI may be performed at screening and/or at any time during the study as clinically indicated

Table 11c. Evaluation and visit schedule for phase 2 of the study

+ / - 1 day window is allowed for cycle 1 procedures. + / - 3 days window is allowed for all subsequent cycles.

Assessment	Screening	Cycle 1		Cycle 2		Cycle 3		Future Cycles (even)(odd)		Progression
Study Day/Visit Day		1 ¹²	8	15	22 ¹³	1	15	1	1	
Informed consent	X									
Background information	X									
Serum Pregnancy Test (WOCBP)	X									
Physical Exam	X	X	X	X	X	X	X	X	X	X
Dermatology Exam	X						X		X	X
Vitals	X	X	X	X	X	X	X	X	X	X
ECOG PS	X	X	X	X	X	X	X	X	X	X
Neuropsychiatric Assessment ¹	X	X		X		X	X	X	X	
Adverse Event Assessment	X	X	X	X	X	X	X	X	X	
Hematology ²	X	X	X	X	X	X	X	X	X	X
HbA _{1c} and C-peptide ³	X				X			(X)	(X)	
Chemistry ⁴	X	X	X	X	X	X	X	X	X	X
Coagulation ⁵	X				X			X		X
Fasting Blood Glucose ⁶	X	X		X		X	X	X	X	
Urinalysis ⁷	X									X
Radiographic Tumor Assessment ⁸	X						X		X	X
RECIST reading	X						X		X	
Tumor Biopsy ⁹	X			X						X
BRAF Testing	X									
MUGA/Echo ¹⁰	X							(X)		
ECG ¹¹	X			X		X	X	(X)	(X)	X

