¹ Symptomatic patients (\geq CTCAE grade 1) must continue with questionnaires on a weekly basis while active on the treatment portion of the study.² Hematology - WBC plus differential (neutrophil including bands, lymphocyte, monocyte, eosinophil, basophil and other counts, hemoglobin and platelets).³ HbA_{1c} and C-peptide will be measured at screening and on Day 1 of every third treatment cycle starting with Cycle 2 Day 1 and at EOT.⁴ Biochemistry - K+, Na+, Ca++, Mg++, LDH, ALT, AST, total bilirubin (direct and indirect), creatinine, amylase, GGT, lipase, alkaline phosphatase (fractionated if alkaline phosphatase is grade 2 or higher), bicarbonate, phosphorus, uric acid, total cholesterol, HDL, LDL, triglycerides, glucose, urea or BUN, albumin, and total protein are required at baseline and at end of treatment. Subsequent assessments always include K+, Na+, Ca++, ALT, AST, total bilirubin (direct and indirect), creatinine, alkaline phosphatase, bicarbonate, phosphorus, glucose, urea or BUN, albumin, and total protein BUT, lipase, total cholesterol, HDL, LDL, triglycerides should be obtained on the first day of odd numbered cycles only.⁵ Coagulation - PT or INR, PTT. Patient entering the study while receiving anti-coagulation therapy or those who have the initiation of an anti-coagulation therapy should have their coagulation test performed on a weekly basis.⁶ Patients must be fasting overnight for at least 8 hours. Additional measurements may be performed as clinically indicated.⁷ Urinalysis includes macroscopic (protein, glucose, ketones, blood, and specific gravity). A microscopic (WBC/HPF, RBC/HPF, and any additional findings) exam need only be performed if the urinalysis result is abnormal.⁸ Screening radiological assessments should be performed within 4 weeks of the first dose. Radiological tumor assessment should be performed at baseline within 28 days before start of treatment and subsequently every 8 weeks of combination therapy (first restaging at the end of week 8), until progression of disease or end of treatment. All assessments should be performed within \pm 7 days of the scheduled day of assessment. The assessment at the end of treatment visit is only to be performed if the prior assessment occurred \geq 21 days before.⁹ Biopsies will be done at Screening, Cycle 1 Day 15, and within 14 days of any radiographic examination documenting disease progression by RECIST from all patients with visible or palpable disease unless the PI determines that a biopsy would pose an unacceptable risk to the patient.¹⁰ Echo/MUGA will be performed at baseline and every 4 cycles, or more often as clinically indicated.¹¹ ECG will be performed at baseline and (+/- 2 days) on cycle 1 day 15, on cycle 2, 3, and 4 day 1, and every 3 months thereafter in accordance with the manufacturer's standard-of-care recommendations for vemurafenib¹² Laboratory assessments including hematology, blood chemistries, and fasting blood glucose do not need to be repeated prior to the first dose of BKM120 if screening laboratories were performed within 72 hours of C1D1.¹³ If toxicity is present at C1D15, C1D22 visit may be done at the discretion of the physician.

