3.4.2 Efficacy assessments

Patients will undergo systemic imaging with a contrast-enhanced CT scan of the chest, abdomen, and pelvis (or a whole body PET/CT scan if this scan includes a CT resolution that is comparable to standard institutional protocols for CT alone) with 28 days prior to the initiation of therapy (baseline imaging) and on the last day of every even-numbered treatment cycle(+/- 3 days). Imaging assessments will be made by a radiologist, and final assessment using Response Evaluation Criteria in Solid Tumors (RECIST, version 1.1) will be made by the PI ^{37,38}. Any documentation of a PR or CR in a target or non-target lesion must be confirmed by a repeat scan at least 4 weeks after the initial scan indicating the PR or CR. The PI bears the final responsibility for determining tumor response and progression.

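### Section 3.4.7 sets the on-treatment pS6 and gene-expression measurements at times (week 4, week 8) for which no biopsy is scheduled; the only scheduled on-treatment biopsy before progression, Cycle 1 Day 15, is named by no analysis

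*Combined protocol and SAP*

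**What the plan says.** **pS6 (section 3.4.7, change in phospho-S6).** H-scores are compared to quantify "pS6 protein levels by IHC prior to treatment at after 8 weeks of treatment". The formula that follows is (H_4w - H_0) / H_0, so its on-treatment term carries a 4-week subscript. The test sentence returns to 8 weeks: the change "over the first 8 weeks of treatment will be compared between the two groups using the Wilcoxon rank-sum test". The two groups are patients who did and did not survive 6 months without progression.

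**Gene expression (section 3.4.7, gene expression profiles).** Profiling is set for cycle 3 day 1 (± 3 days) and within 7 days of determining progression, with the pre-treatment profile as reference. Hypothesis 1 concerns RECIST response after 8 weeks. The initial goal is matched specimens from 10 patients: 5 who meet 6-month PFS and 5 who progress within 4 months. Further biopsies are allowed at the PI's discretion.

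**Biopsy schedule.** Section 3.4.7 opens with: "Biopsies of palpable melanoma lesions and nodal metastases will be taken at baseline, on Cycle 1 Day 15". The window for that visit is ± 3 days. The third and last time is progression, with tissue due no later than 14 days after imaging shows it. Footnote 9 of Tables 11a, 11b and 11c agrees: "Biopsies will be done at Screening, Cycle 1 Day 15, and within 14 days of any radiographic examination documenting disease progression by RECIST". The Tumor Biopsy row of each table has marks at those three times and no others.

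Sections 5.1 and 5.3 refer to section 3.4.7 for the statistical plan of these assessments and add nothing on timing.

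**The concern.** The pS6 paragraph gives two on-treatment times for one variable, and neither has a scheduled specimen. The expression paragraph uses a time that also has none. The one on-treatment biopsy that every patient with accessible disease is due, at Cycle 1 Day 15, is named by no stated analysis.

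Two phase 2 secondary objectives are at stake: objective 4 (pathway reduction and PFS) and objective 5.i (responding tumours lacking both signatures). For objective 4 the gap is also tied to the outcome. The scheduled tissue nearest week 8 is progression tissue, so under the schedule a patient has a specimen near that time only by having failed the endpoint that defines the groups. Leaving 2, 4 and 8 weeks all open also permits a choice of time point after the data are seen.

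**Working it through.** The plan states no figure to reproduce. The check converts each named time to a study day and asks whether any window joins a named analysis time to a scheduled biopsy.

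**Inputs**
- Cycle length: 28 days (section 3.1). Restaging "on the last day of every even-numbered treatment cycle" (section 3.4.2) and every 8 weeks (Table 11 footnote 8) agree with this.
- Biopsy at Cycle 1 Day 15, ± 3 days (section 3.4.7).
- Expression at cycle 3 day 1, ± 3 days (section 3.4.7).
- Restaging window: ± 7 days (footnote 8) or ± 3 days (section 3.4.2). Progression biopsy: within 14 days.

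**Study days**, with study day = (cycle - 1) × 28 + day:
- Cycle 1 Day 15 = Day 15; window Days 12-18.
- Week 4 = Day 28 (end of the week) or Day 29 (four weeks after Day 1).
- End of week 8 = Day 56. Cycle 3 day 1 = 2 × 28 + 1 = Day 57; window Days 54-60. These are one time point in practice.

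**Gaps from the latest in-window Cycle 1 Day 15 biopsy (Day 18)**
- To week 4: 28 - 18 = 10 days, or 29 - 18 = 11 days.
- To the opening of the cycle 3 day 1 window: 54 - 18 = 36 days.

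**Who has tissue near week 8 under the schedule**
- Patients progressing at the first restaging (Day 56). With ± 7 days, scans fall on Days 49-63 and tissue is due by 63 + 14 = Day 77 at the latest. With ± 3 days, scans fall on Days 53-59 and tissue is due by 59 + 14 = Day 73.
- At scheduled restagings, all other patients have no further tissue due before the second one (end of week 16, Day 112), whose window opens on Day 112 - 7 = 105 or Day 112 - 3 = 109.
- Patients who reach 6 months progression-free have no radiographic progression in that time, so their only scheduled on-treatment tissue is the Cycle 1 Day 15 biopsy.

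**Side by side**

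| Item | Time named | Biopsy scheduled then? |
|---|---|---|
| pS6 text and Wilcoxon sentence | week 8 | no |
| pS6 formula | week 4 | no |
| On-treatment expression profile | cycle 3 day 1 (week 8) | no |
| Biopsy at Cycle 1 Day 15 | week 2 | yes, but no analysis names it |

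The success group of the Wilcoxon comparison therefore has no scheduled specimen at week 4 or week 8. The 5 planned 6-month-PFS patients in the expression study have none at cycle 3 day 1. Objective 5.ii, on progressing tumours, can use the progression biopsies.

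**The case against.** **The expression paragraph may itself order tissue on cycle 3 day 1.** This is a fair reading, and several statements point to week 8: the pS6 text, the Wilcoxon sentence, hypothesis 1 and the cycle 3 day 1 profile. If it is right, the opening of section 3.4.7 and all three tables omit a required biopsy, and H_4w is still wrong. The documents do not say which text prevails, so the need to reconcile them stands.

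**H_4w may be a slip.** Perhaps, but changing it to 8 weeks leaves no scheduled specimen behind it.

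**The PI may take extra biopsies.** That permits biopsies and schedules none. Tissue taken at discretion would come from a selected subset.

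**Stronger readings that a reader might infer, and that the documents do not support**
- *That the Cycle 1 Day 15 window is contradictory* (± 3 days in section 3.4.7, ± 1 day in the Table 11c header). A biopsy-specific window can override a general header, as the ± 2 days for the Cycle 1 Day 15 ECG in footnote 11 already does. One confirming line is enough.
- *That the 7-day and 14-day progression limits conflict.* The first governs when expression is determined, counted from the determination of progression. The second governs when the biopsy is taken, counted from radiographic progression. The clocks may start on different days, and both limits can be met together.
- *That outcome-dependent sampling undermines all of objective 5.* The 10-patient expression plan selects its groups by outcome on purpose. Its gap is missing on-treatment tissue from non-progressors; the dependence argument belongs to pS6.
- *That the consent form must change.* The consent pages were not available, so this cannot be judged.

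**Conclusion.** The mismatch is real: three on-treatment times (2, 4 and 8 weeks) appear, the analyses use the two without a scheduled biopsy, and the windows miss by at least 10 days (week 4) and 36 days (cycle 3 day 1). If the schedule is followed, objectives 4 and 5.i cannot be run as written.

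This rests on 28-day cycles without delay and on the schedule tables governing tissue collection. No number of affected patients can be given, because biopsy is limited to visible or palpable disease, can be waived and is otherwise optional, and no biopsy-evaluable fraction is stated.

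The effect is confined to these secondary correlative analyses. A reader should not extend it to the primary 6-month PFS endpoint, the sample size or the decision rule, none of which uses on-treatment tissue.

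**What to change.** Before data are seen, make the pS6 text, the formula subscript, the Wilcoxon sentence, the expression time point and the biopsy schedule name one specimen. Two routes are open.

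- **(a) Cycle 1 Day 15.** Define the pS6 change and the on-treatment expression profile on the already scheduled Cycle 1 Day 15 biopsy against baseline, and keep the Wilcoxon rank-sum test. Cost: wording in section 3.4.7 only. Downside: it measures 2-week rather than 8-week suppression, so hypothesis 1 would relate early suppression to later response.
- **(b) Week 8.** If this was intended, change H_4w to match, and bring the biopsy paragraph of section 3.4.7 and Tables 11a-c into line with that time point. Cost: one more biopsy than the current schedule carries, for patients with visible or palpable disease. This is the investigators' decision.

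Two minor clarifications apply on either route: confirm that the ± 3 day biopsy window overrides the ± 1 day Table 11c header, and align the 7-day expression limit with the 14-day progression-biopsy window.

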3.5 Treatment compliance

Records of study medication used, dosages administered, and intervals between visits will be recorded during the study. Drug accountability will be noted and patients will be asked to return all unused study medication.

3.6 Safety monitoring plan

3.6.1 Safety assessments

Safety assessments will consist of monitoring and recording all adverse events and serious adverse events, the regular monitoring of hematology, blood chemistry and urine values, regular measurement of vital signs and the performance of physical examinations. Dermatologic assessments will be performed at screening, on week 3 day 1, and at every 8 week intervals thereafter.

These assessments should be performed within ± 1 day (during DLT period) or ± 3 days (all subsequent cycles) of the scheduled day of assessment except for adverse events that will be evaluated continuously through the study. Safety and tolerability will be assessed according to the NIH/NCI CTC:

http://ctep.cancer.gov/protocolDevelopment/electronic_applications/ctc.htm

3.6.2 Adverse events

Information about all adverse events, whether volunteered by the subject, discovered by investigator questioning, or detected through physical examination, laboratory test or other means, will be collected and recorded and followed as appropriate.

An adverse event is the appearance or worsening of any undesirable sign, symptom, or medical condition occurring after starting the study drug even if the event is not considered to be related to study drug. Medical conditions/diseases present before starting study drug are only considered adverse events if they worsen after starting study drug. Abnormal laboratory values or test results constitute adverse events only if they induce clinical signs or symptoms, are considered clinically significant, or require therapy.

The occurrence of adverse events should be sought by non-directive questioning of the patient at each visit during the study. Adverse events also may be detected when they are volunteered by the patient during or between visits or through physical examination, laboratory test, or other assessments. As far as possible, each adverse event should be evaluated to determine:

1. the severity grade (mild, moderate, severe) or (grade 1-4)
2. its relationship to the study drug(s) (suspected/not suspected)
3. its duration (start and end dates or if continuing at final exam)
4. action taken (no action taken; study drug dosage adjusted/temporarily interrupted; study drug permanently discontinued due to this adverse event; concomitant medication taken; non-drug therapy given; hospitalization/prolonged hospitalization)
5. whether it constitutes a serious adverse event (SAE)

All adverse events should be treated appropriately. Such treatment may include changes in study drug treatment including possible interruption or discontinuation, starting or stopping concomitant treatments, changes in the frequency or nature of assessments, hospitalization, or any other medically required intervention. Once an adverse event is detected, it should be followed until its resolution, and assessment should be made at each visit (or more frequently, if necessary) of any changes in severity, the suspected relationship to the study drug, the interventions required to treat it, and the outcome.

Information about common side effects already known about BKM120 can be found in the Investigators' Brochure and additional data regarding vemurafenib can be found in the published literature. This information should be included in the patient informed consent and should be discussed with the patient during the study as needed.

Adverse Event Monitoring: Adverse events (AEs) will be recorded on the OnCoreeResearch database, all grade 3-5 expected and unexpected AEs will be recorded and updated at each visit.

3.6.3 Serious adverse events

A serious adverse event is an undesirable sign, symptom or medical condition which:

- is fatal or life-threatening
- results in persistent or significant disability/incapacity
- constitutes a congenital anomaly/birth defect
- requires inpatient hospitalization or prolongation of existing hospitalization, unless hospitalization is for:
 - routine treatment or monitoring of the studied indication, not associated with any deterioration in condition
 - elective or pre-planned treatment for a pre-existing condition that is unrelated to the indication under study and has not worsened since the start of study drug
 - treatment on an emergency outpatient basis for an event not fulfilling any of the definitions of a SAE given above and not resulting in hospital admission
 - social reasons and respite care in the absence of any deterioration in the patient's general condition
 - is medically significant, i.e., defined as an event that jeopardizes the patient or may require medical or surgical intervention to prevent one of the outcomes listed above

To ensure patient safety, every SAE, **regardless of suspected causality**, occurring

- after the patient has provided informed consent and until 4 weeks after the patient has stopped study treatment/participation
- after the patient is randomized and until 4 weeks after the patient has stopped study treatment
- after the patient begins taking study drug and until 4 weeks after the patient has stopped study treatment
- after protocol-specified procedures begin (e.g., placebo run-in, washout period, double-blind treatment, etc.) and until 4 weeks after the patient has stopped study treatment
- after the start of any period in which the study protocol interferes with the standard medical treatment given to a patient (e.g., treatment withdrawal during washout period, change in

treatment to a fixed dose of concomitant medication) and until 4 weeks after the patient has stopped study treatment must be reported to Novartis within 24 hours of learning of its occurrence. Any SAEs experienced after this 4-week period should only be reported if the investigator suspects a causal relationship to the study drug. Recurrent episodes, complications, or progression of the initial SAE must be reported as follow-up to the original episode within 24 hours of the investigator receiving the follow-up information. An SAE occurring at a different time interval or otherwise considered completely unrelated to a previously reported one should be reported separately as a new event.

